11.2 Calculation or derivation of safety variable(s)

11.2.1 Other significant adverse events (OAE)

During the evaluation of the AE data, an AstraZeneca medically qualified expert will review the list of AEs that were not reported as SAEs or Discontinuation of Investigational Product due to Adverse Event (DAE)s. Based on the expert's judgement, significant adverse events of particular clinical importance may, after consultation with the Global Patient Safety Physician, be considered OAEs and reported as such in the Clinical Study Report. A similar review of laboratory, vital signs and dECG data will be performed for identification of OAEs.

Examples of these are marked haematological and other laboratory abnormalities, and certain events that lead to intervention (other than those already classified as serious), dose reduction or significant additional treatment.

11.3 Calculation or derivation of patient reported outcome variables

To be eligible for randomisation the patients must have reported symptoms in the RESQ-7 (7 days recall) a minimum of 3 days and a rating of at least mild intensity on at least one of the following items;

- a burning feeling behind the breastbone
- unpleasant movement of material upwards from the stomach.

The patient diary used during impedance/pH measurements (see [appendix H](#)) will be analysed and evaluated in connection to the assessment of the results by the central reader.

The patients use of the data logger and recording on the diary card for meal intake and periods in supine position as well as symptoms will be used for determination of; relation between reflux episodes and symptoms during the 24-hours.

11.4 Calculation or derivation of pharmacokinetic variables

The pharmacokinetic analyses will be performed at AstraZeneca R&D, Mölndal, Sweden, by standard non-compartmental methods using WinNonlin Enterprise.

The actual sampling times, if different from protocol times, will be used in the final pharmacokinetic calculations. Plasma concentrations below LLOQ will be excluded except for the pre-dose samples after the first dose, which will be taken as zero. Furthermore, if there are more than one plasma concentration below LLOQ prior to C_{max} , then the last one before the first measurable plasma concentration will be calculated as LLOQ/2. The following PK parameters will be determined:

Table 6 Pharmacokinetic parameters to be determined in the study

Parameter	Description
AUC_{0-12h}	The area under the plasma concentration-time curve from time 0 to 12 hours after the first dose of AZD3355 calculated by the log/linear trapezoidal method
AUC_{12-24h}	The area under the plasma concentration-time curve from time 12 to 24 hours after the first dose (0-12 hours after the second dose) of AZD3355 calculated by the log/linear trapezoidal method
AUC_{0-24h}	The sum of AUC_{0-12h} and AUC_{12-24h} after the first and second doses of AZD3355
C_{max}	The observed maximum plasma concentration after each dose of AZD3355
t_{max}	The time to reach C_{max} after each dose of AZD3355

11.5 Calculation or derivation of pharmacodynamic variables

See also Section 6.3.1.1.

Relationship between AZD3355 exposure and effect on impedance measurements will be presented graphically. If appropriate, exposure-effect relationship will be further explored.

11.6 Calculation or derivation of pharmacogenetic variables (Not applicable)

11.7 Calculation or derivation of health economic variables (Not applicable)

12. STATISTICAL METHODS AND SAMPLE SIZE DETERMINATION BY ASTRAZENECA

12.1 Description of analysis sets

12.1.1 Efficacy analysis set

The evaluation of the efficacy of AZD3355 30 mg, 90 mg, 120 mg, 240 mg and placebo, will be based on all patients and data not affected by major protocol deviations and violations, relevant for the analysis of a specific variable.

The PK Analysis Set will be a subset of the Safety Analysis Set and will include only subjects with no major protocol deviations thought to significantly affect the PK (eg, subject vomited at or before 2 times median t_{max} ; wrong dose administered; prohibited concomitant medication, etc.). A strategy for dealing with protocol deviations will be specified prior to clean file by the Study Delivery Team (SDT Leader, Physician, Pharmacokineticist and Statistician).

The evaluability of the data will be determined and documented prior to starting the statistical analysis (and before database lock).

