Pharmacokinetic (PK) samples as well as sitting BP and pulse should be taken from pre-dose until 24 hours after the first dose (for detailed time of PK samples, BP and pulse see Table 2). During the early morning PK sampling the patient should be encouraged to stay in supine position until their normal waking time

The patient will eat a standardized meal approximately one hour after each dose of AZD3355 and at the same time points during the different study periods. The meals (food and liquid) will be standardized primarily regarding fat content and pH. The patient should be encouraged to complete the meal. If not possible, the same amount should be eaten at each meal during

each study period. During the stay in the clinic the patients should be encouraged to move around to mimic normal activities as much as possible.

Day 2: In the morning of day two, the last PK sample and a reduced safety lab screen will be collected. Sitting BP and pulse is measured before the patients leaves the clinic.

The active questioning for specific symptoms will take place again (see Section [6.4.3.2](#)) before the patient leaves in the mornings after the impedance is completed, but before the catheter is removed.

No antacids are allowed 24 hours before and during the treatment period (due to interference with pH measurement). The 4 study periods will be separated by a washout period of 7-28 days.

Adverse events (AEs) will be recorded after drug administration at Visit 2 throughout the study.

Table 2 Study period procedures

Time post dose (h:min)	Clock Time^a (h:min)	PK blood sample^b (No)	Blood pressure and pulse monitoring^c	Activity
Day 1				
Pre-dose	07:00	1	Sitting, supine and standing after 1 min	BP, pulse, dECG, orthostatic test, reduced laboratory screen, PGx ^e urine sample for drug abuse screen ^d Placement of impedance/pH catheter
0:00	08:00			Active question specific symptoms Drug/placebo administration Start of impedance/pH recording
0:30	08:30	2		
1:00	09:00			Breakfast
1:30	09:30	3		
2:00	10:00	4	Supine + standing after 1 min	dECG, orthostatic test
2:30	10:30	5		
4:00	12:00	6	Sitting	
4:30	12:30			Lunch
8:00	16:00	7	Sitting	Snack
12:00	20:00	8	Sitting	Drug/placebo administration
12:30	20:30	9		
13:00	21:00			Evening meal
13:30	21:30	10		
14:00	22:00	11	Sitting	
14:30	22:30	12		
Day 2				
16:00	00:00	13		
21:00	05:00	14		

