5.6.2 Doses and treatment regimens

Blinded study medication will be taken orally, twice daily. One dose will consist of 2 capsules. Patients will be instructed to take the 2 capsules from the AM bottle in the morning and the 2 capsules from the PM bottle in the evening, see [Table 2](#) for details.

Patients will be randomised at Visit 2 to 1 of 5 treatment groups, 30 mg AZD3355, 90 mg AZD3355, 120 mg AZD3355, 240 mg AZD3355 or placebo for 1 day of that treatment. Treatment will be given as follows:

Both AM and PM bottles will contain 2 capsules of drug, either AZD3355 30 mg, 60 mg, 120 mg or matching placebo or a combination (see below).

- Treatment A: One 30 mg capsule + One placebo capsule
- Treatment B: One 30 mg capsule + One 60 mg capsule
- Treatment C: One 120 mg capsule + One placebo capsule
- Treatment D: One 120 mg capsule + One 120 mg capsule
- Treatment E: One placebo capsule + One placebo capsule.

This is a 4-way crossover study so each patient will receive placebo and 3 of the 4 doses of AZD3355 in a randomised order. At visits 3, 4 and 5 patients will crossover to one of the other treatment groups according to the randomisation scheme from Visit 2.

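### The PK analysis set is defined by subject, so in this crossover a deviation confined to one dose removes three active profiles where only one is affected

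*Protocol*

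**What the plan says.** Section 12.1.1 of the protocol, under the heading for the efficacy set, defines two sets.

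- **Efficacy set.** The evaluation "will be based on all patients and data not affected by major protocol deviations and violations, relevant for the analysis of a specific variable". Because the unit is patients and data, a single period can be left out.
- **PK set.** It is a subset of the safety set and "will include only subjects with no major protocol deviations thought to significantly affect the PK". The unit is the subject. The examples are that the "subject vomited at or before 2 times median" tmax, that a wrong dose was given, or that a prohibited medication was taken.

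The next sentence adds: "A strategy for dealing with protocol deviations will be specified prior to clean file by the Study Delivery Team". The section then says that evaluability of the data is settled before analysis and database lock.

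On the design, section 5.6.2 says that "each patient will receive placebo and 3 of the 4 doses of AZD3355 in a randomised order", and section 3.1 says: "The 4 study periods will be separated by a washout period of 7-28 days". Table 6 in section 11.4 defines the PK parameters by dosing interval: AUC0-12h belongs to the first dose and AUC12-24h to the second, and Cmax is "The observed maximum plasma concentration after each dose of AZD3355".

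**The concern.** Two of the three example deviations are events of a single dose. Vomiting after one capsule intake says nothing about a profile taken at least a week earlier or later. A subject-level rule still removes that profile, because the patient is no longer a subject without a major deviation.

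The two sets in section 12.1.1 would also treat the same event differently. A patient's reflux counts from unaffected periods can stay in the efficacy set while the valid AUCs from those periods leave the PK set.

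Two secondary objectives in section 2.2 are at stake: the PK at each of the four doses, and the relation of AUC to reflux episodes. With 14 to 16 evaluable patients planned per dose, each profile dropped without need is noticeable.

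**Working it through.** **Inputs**

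- Ten sequences, section 5.3.1: EABC, ABCE, BCED, CEDB, EDBA, DABE, ABEC, BECD, ECAD, CADE (A = 30, B = 90, C = 120, D = 240 mg, E = placebo).
- 20 evaluable patients targeted and 27 randomised, section 12.3.
- 15 PK samples per period (Table 2), which gives the 60 per patient in Table 5.
- Deviation rate: none in the protocol. I assume p = 1% to 10% per active period, independent between periods.

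**Reproducing the plan's own figure.** Counting letters over the ten sequences gives A 7, B 8, C 8, D 7, E 10. With two patients per sequence this is 14, 16, 16, 14 and 20, which matches section 12.3. Active profiles: 14 + 16 + 16 + 14 = 60 for 20 patients. For 27 patients who all complete, 27 × 3 = 81.

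**One affected patient.** The subject rule loses 3 active profiles (45 samples). A period rule loses 1 (15 samples). The difference is 2 valid profiles (30 samples).

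**Expected loss over the study**

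- Period rule: 3Np.
- Subject rule: 3N[1 − (1 − p)³], because a patient is dropped if any of the three active periods has a deviation.

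Example, N = 20 and p = 5%: the period rule loses 60 × 0.05 = 3.0. The subject rule loses 60 × (1 − 0.95³) = 60 × 0.142625 = 8.6.

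| Assumed p | N = 20, period | N = 20, subject | N = 27, period | N = 27, subject |
|---|---|---|---|---|
| 1% | 0.6 | 1.8 | 0.81 | 2.4 |
| 2% | 1.2 | 3.5 | 1.62 | 4.8 |
| 5% | 3.0 | 8.6 | 4.05 | 11.6 |
| 10% | 6.0 | 16.3 | 8.1 | 22.0 |

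The subject rule loses 2.97 times as many profiles at p = 1% and 2.71 times as many at p = 10%.

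**If deviations occurred only at 240 mg** (14 of 20 patients; assumed rates 5%, 10%, 20%). Profiles properly excluded at 240 mg: 14 × rate = 0.7, 1.4, 2.8. Every patient on 240 mg has two other active periods, so the valid profiles lost at 30, 90 and 120 mg are twice that: 1.4, 2.8, 5.6.

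**The case against.** The strongest reply is that the sentence is generic wording and not the last word. A team that includes the pharmacokineticist and the statistician is to set a deviation strategy before clean file. Evaluability is to be judged on data, and section 5.5.2 puts those decisions before the codes are broken. Section 5.8 defines compliance for each study period, and section 12.2 refers further detail to a statistical analysis plan that is not shown. All of this leaves room for exclusion by period. It does not change the definition, though: none of these sentences says that exclusion is by period, and the protocol states a subject rule where it could have stayed silent.

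A reader might go further and infer that the rule selectively removes the patients who tolerate the drug worst, and so biases the PK results. The protocol does not support that as a statement of fact. Only vomiting, one of three examples, could reflect tolerability; a wrong dose or a prohibited medication need not. No vomiting rate is given, and vomiting is not among the common adverse events listed in section 1.4. Selection is therefore conditional, and its direction is unknown.

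The reply is also right that the consequence is limited. Section 11.5 plans a graphical display of exposure and effect, with more only if appropriate, and does not say that the display is restricted to the PK set. No formal PK test or power statement appears. Finally, a period rule does not cure selection at the affected dose, since that profile is excluded under either rule.

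**Conclusion.** The point holds as a matter of efficiency and consistency. Read as written, section 12.1.1 discards two valid active profiles for each patient with a deviation confined to one active period. In expectation this is 1.8 to 16.3 of 60 profiles against 0.6 to 6.0 under a period rule, for assumed rates of 1% to 10%. At the low end the two rules differ by only 1.2 profiles. These figures rest on the assumed rate, on independence between periods, and on a strict reading of the subject rule. If deviations cluster in the same patients, the gap narrows.

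The cost is precision in the secondary per-dose PK summaries and, where they use this set, in the exposure-reflux analyses. The primary dose-response analysis uses the efficacy set and is not touched. Bias from selection is a possibility only if the deviations relate to tolerability or dose. The change is worth considering; the plan does not fail without it.

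**What to change.** In section 12.1.1, replace subjects by patient-periods in the PK set definition and have the Study Delivery Team's blinded deviation strategy apply the same rule:

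- Exclude only the affected period, and keep the patient's other periods.
- Within a period, keep the parameters of an interval that is clearly unaffected. If the deviation follows the second dose, AUC0-12h stays, while AUC12-24h, AUC0-24h and the second-dose Cmax and tmax go. After a first-dose deviation, check AUC12-24h before keeping it, because a lost first dose can lower it through reduced carry-over.
- Summarise a wrong-dose profile under the dose actually taken, as section 12.1.2 already does for safety.
- Allow wider exclusion where a deviation, such as prohibited medication, spans periods.

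The cost is about one sentence, plus period and interval flags in the PK dataset; no new data are needed. The downside is that numbers will differ between parameters and doses, and the patients summarised at one dose may not be those summarised at another. The report should show the count behind each summary.

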12.1.2 Safety analysis set

All patients who received at least one dose of AZD3355 or placebo and for whom post-dose data are available will be included in the safety analysis set. Throughout the safety results sections, erroneously treated patients (eg, those randomised to treatment A but actually given treatment B) will be accounted for in the actual treatment group.

12.2 Methods of statistical analyses

The estimation of the dose-response curve will primarily be made by estimating the parameters of a fixed effect Emax model. In addition, the same model will be estimated with data from study [D9120C00020](#) (using 65 mg bid) included with a mixed effect Emax model with and without data from [D9120C00020](#) included. The possibility of using additional model will also be explored. The data will be logarithmically transformed prior to estimation of the dose-response curves. If zero values are obtained during a period then the logarithm is undefined and no transformation prior to analysis will be made. If the logarithmic transform is used the estimated mean curves and 2-sided 90% confidence interval (CI) limits will be transformed back to the original scale to give geometric mean curves and corresponding confidence intervals.

The effect of 4 different doses of AZD3355 measured as reduction in the total number of reflux episodes during 24 hours (total, upright and supine position), compared to placebo will be assessed by estimating the inhibition (%) in the primary variables after treatment with AZD3355 30 mg, 90 mg, 120 mg and 240 mg compared to placebo. Inhibition defined as $100 \times (1 - R)$ where R is the ratio (AZD3355/placebo) of estimated geometric means. The estimated geometric means for each treatment (AZD3355 30 mg, 90 mg, 120 mg and 240 mg and placebo) will also be presented. For estimating the geometric means the data will be logarithmically transformed prior to statistical analysis. If zero values are obtained during a period then the logarithm is undefined and no transformation prior to analysis will be made. Then the primary objective will be assessed by the differences in arithmetic means.

The analysis will be based on an mixed effect model with treatment, period and sequence as fixed effects and patient as a random effect. If the logarithmic transform is used the estimated arithmetic means and their differences and 2-sided 90% confidence interval (CI) limits will be transformed back to the original scale to give geometric means, ratios and corresponding confidence intervals. The same analysis will be made for the other variables addressed in the secondary objective.

No correction for multiplicity will be made.

Further details of the statistical analysis will be given in the Statistical Analysis Plan.

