3.2 Rationale for study design, doses and control groups

The doses were selected in order to evaluate the effect of AZD3355 in a dose range from 30 mg to 240 mg bid, in order to evaluate doses both higher and lower than the 65 mg bid dose that was used in study [D9120C00020](#). The 240 mg bid dose was chosen in order to evaluate the effect at the highest possible therapeutic dose. In order to estimate the efficacy and compare and assess safety information for AZD3355 each patient will receive placebo in addition to 3 of the 4 doses of AZD3355.

The study population was chosen to resemble the study population in [D9120C00020](#) which allowed mild symptoms for three days. Therefore, the study population will not be exactly comparable with the study population in the planned dose finding study ([D9120C00019](#)) where only patients with persistent symptoms of moderate severity will be included. Although symptoms are not the primary endpoint to this study, the information on the effect of AZD3355 on reflux episodes is still valuable in understanding if there is a dose relationship in patients who have reflux irrespective of the symptom burden.

The double-blind, cross over design was chosen in order to avoid bias and reduce variability and thereby sample size. Placebo was included as a comparator to determine the difference between PPI alone and the addition of AZD3355. The sample size was based on previous experience in a similar setting.

The effect on reflux as measured by 24h combined impedance/pH registration was chosen as primary endpoint since it is believed that AZD3355 reduces the total number of reflux episodes, whether the reflux is acid, weakly acidic or weakly alkaline. Symptoms are thought to be produced by the refluxate in the esophagus therefore, decreasing the number of reflux episodes should impact on the symptom burden of patients who have GERD and are partial responders to PPI treatment. Further, intragastric pH will be monitored to evaluate if AZD3355 has an effect on gastric acid secretion, as has been suggested in some animal studies, and can reduce the time with pH<4 in the dose range used in the study.

Genetic samples will be collected for future exploratory research into genes/genetic variation that may influence response (ie, PK profile, safety, tolerability and efficacy) to AZD3355 and/or agents used in combination and/or as comparators and/or susceptibility to GERD.

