12.3 Determination of sample size

In study [D9120C00020](#) the between and within-subject standard deviation (STD) for the logarithm of total number of reflux episodes during 24 hour ambulatory impedance monitoring was estimated to 0.79 and 0.25, respectively, using 21 evaluable patients. The geometric mean number of total number of reflux episodes was 30.6 (95% CI 20.9, 44.7) for AZD3355. This corresponded to a distance between the upper and lower 95% CI for the estimated mean of the logarithm of the total number of reflux episodes during 24 hours of 0.77. This precision was regarded as satisfactory.

By simulation of data with this variability, 20 patients and the treatment sequence used here, the width of the 95% CI for the estimated mean curve of the Emax model and the mixed effect Emax model was estimated to 0.70 and 1.73, respectively. When the data from [D9120C00020](#) was added to the simulated data, the width was estimated to 0.53 and 1.43, respectively. For a geometric mean of 30.6 these widths would correspond to 95% CI of (23.5, 39.9) and (15.0, 62.6), respectively.

With 20 randomised patients, all will be assigned to placebo, 14 will be assigned to AZD3355 30 mg, 16 will be assigned to AZD3355 90 mg, 16 will be assigned to AZD3355 120 mg and 14 will be assigned to AZD3355 240 mg. In order to achieving these numbers of evaluable patients on each of the doses the study will include 27 randomised patients.

The number of patients that will agree to participate in the genetic research is unknown. It is therefore not possible to establish whether sufficient data will be collected to allow a formal statistical evaluation or whether only descriptive statistics will be generated. A statistical analysis plan will be prepared where appropriate.

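### The primary dose-response fit is a fixed-effect Emax model that, on the natural reading, has no patient term, so its standard errors do not suit a crossover with intra-patient correlation 0.91

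*Protocol*

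**What the plan says.** Section 12.2 of the protocol designates the primary dose-response analysis: "The estimation of the dose-response curve will primarily be made by estimating the parameters of a fixed effect Emax model". Among the additional analyses, the same model is to be fitted with the earlier 65 mg bid study (D9120C00020) "included with a mixed effect Emax model with and without data from" that study. For the Emax fits, the planned output is the curve itself: "the estimated mean curves and 2-sided 90% confidence interval (CI) limits will be transformed back" to the original scale.

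The dose-versus-placebo comparisons, reported as inhibition (%), use a different model: "The analysis will be based on an mixed effect model with treatment, period and sequence as fixed effects and patient as a random effect".

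Section 12.3 gives the variability from D9120C00020. The between- and within-subject SDs of the log count "was estimated to 0.79 and 0.25, respectively, using 21 evaluable patients". For 20 simulated patients, the 95% CI width for the mean curve of the "Emax model and the mixed effect Emax model was estimated to 0.70 and 1.73, respectively". With D9120C00020 added, the widths become 0.53 and 1.43. Section 3.2 gives the reason for the design: "The double-blind, cross over design was chosen in order to avoid bias and reduce variability and thereby sample size".

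**The concern.** The primary objective is the dose-response relationship, and each patient gives four recordings, one of them on placebo. With these SDs, about 91% of the variance of a single recording lies between patients. An Emax fit without a patient term puts that variance into the standard error of every dose comparison and of Emax and ED50. It also treats four recordings from one patient as four independent ones, which overstates the information about the mean level. The two errors run in opposite directions, so the primary curve could show an interval that is too tight where the doses cluster, alongside parameters that look far less certain than the data warrant.

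Section 12.3 adds to the problem. It sets 0.70 beside 1.73, which makes the fixed-effect fit look much the more precise of the two.

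**Working it through.** **Inputs.** SDs 0.79 and 0.25, 20 patients and the stated widths (Section 12.3); the ten sequences (Section 5.3.1); ratio 0.61 to placebo at 65 mg bid over 24 hours (Section 1.3). ED50 is not given. I assume 15 to 240 mg and fix the curve at 0.61 for 65 mg, so Emax = ln(0.61) × (65 + ED50)/65. At ED50 65 mg this is −0.494 × 2 = −0.99.

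**Step 1. Reproduce the protocol's own figures.**
- Total SD = √(0.79² + 0.25²) = √0.6866 = 0.829. Intra-patient correlation = 0.6241/0.6866 = 0.91.
- Reference width: 2 × 2.086 × 0.829/√21 = 0.75. The protocol states 0.77, for "The geometric mean number of total number of reflux episodes was 30.6 (95% CI 20.9, 44.7) for AZD3355"; ln(44.7/20.9) = 0.76.
- The ten sequences, each used twice, give 20 patients on placebo and 14, 16, 16 and 14 on 30, 90, 120 and 240 mg, as stated.
- Widths 0.53 and 1.43 around 30.6 give (23.5, 39.9) and (15.0, 62.6), as stated.

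**Step 2. Which model gives 0.70?** Linearise the curve with g(d) = (1, d/(ED50+d), −Emax·d/(ED50+d)²), and let X hold these rows. V has 0.79² between recordings of one patient, with 0.25² added on the diagonal.
- No patient term, reported: 0.6866 (X′X)⁻¹
- No patient term, true: (X′X)⁻¹ X′VX (X′X)⁻¹
- Random patient intercept: (X′V⁻¹X)⁻¹

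95% mean-curve widths over ED50 15 to 240 mg (t quantiles):

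| Model | 20 patients | With D9120C00020 |
|---|---|---|
| Stated, fixed effect | 0.70 | 0.53 |
| No patient term | 0.69–0.74 at placebo; 0.43–0.86 over all doses | 0.50–0.51 at placebo; mean over doses 0.51 |
| Random intercept | 0.72–0.75 | 0.50–0.57 |
| Patient as fixed effects | 0.13–0.27 | – |
| Stated, mixed effect | 1.73 | 1.43 |

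With normal quantiles the 20-patient random-intercept widths are 0.70 to 0.74. So 0.70 rules out patient fixed effects. It fits a model with no patient term, and it would also fit a random intercept. A random intercept alone does not give 1.73 or 1.43.

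**Step 3. Dose contrasts and parameters.** For two treatments in the same patients, the reported-SE ratio is 0.829/0.25 = 3.31. For the Emax curve with 20 patients and ED50 65 mg:

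| Dose vs placebo | SE, no patient term | SE, random intercept | Ratio | True SE of no-patient fit ÷ random intercept |
|---|---|---|---|---|
| 30 mg | 0.231 | 0.071 | 3.25 | 1.55 |
| 90 mg | 0.234 | 0.071 | 3.31 | 1.10 |
| 120 mg | 0.226 | 0.068 | 3.31 | 1.06 |
| 240 mg | 0.257 | 0.079 | 3.23 | 1.65 |

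Over ED50 15 to 240 mg, the reported ratio is 3.2 to 3.3 for contrasts and 3.1 to 3.2 for Emax and ED50. The true ratio is 1.0 to 1.8 for contrasts and 1.9 to 2.1 for ED50. At ED50 65 mg, the SE of ED50 is 102 mg as reported, 64 mg in truth, and 32 mg with a random intercept.

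**Step 4. Mean curve.** Reported SE divided by true SE of the fit without a patient term, ED50 15 to 240 mg: 0.92 to 1.00 at placebo, 0.60 to 0.78 at 65 to 120 mg, and 0.80 to 0.98 at 240 mg. At 30 mg it depends on the assumed ED50 (0.66 to 0.96). In simulation (300 nonlinear fits per setting, 20 and 27 patients, ED50 30 to 120 mg), nominal 95% intervals covered about 74% to 86% at 65 to 120 mg and 90% to 94% at placebo and 240 mg. The random-intercept fit covered about 94% to 98%.

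The ratios do not depend on whether 90% or 95% intervals are used, and those for 27 patients are nearly the same.

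**The case against.** The strongest reply is that the protocol never says in words that the primary model lacks a patient term. Fixed versus mixed could separate common from patient-specific Emax and ED50, with a patient intercept in both. A random intercept yields about the stated 0.70 and 0.53, so a reader who infers that Section 12.3 proves the absence of a patient term goes too far. This stands. What remains is the plain contrast in Section 12.2, and the fact that the same section names patient as a random effect where it wants one.

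Second, a reader might infer that the reported dose effects will have intervals three times too wide. They will not. Inhibition (%) and its intervals come from the separate model with patient as a random effect. The factor of about 3.2 applies only to Emax, ED50 and contrasts taken from the primary curve. It compares reported SEs, not information lost. Nor is the crossover discarded throughout: that separate model uses it, and a mixed-effect Emax fit is already planned.

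Third, 1.73 might be taken as a mistake. Section 12.3 does not say which parameters were random, and random Emax or ED50 could widen the interval. The figure is unexplained, not shown wrong. Nothing in the protocol says the widths decided the choice of primary model.

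Fourth, this is a phase IIA estimation study with no test tied to the curve, and Section 12.2 defers further details to the SAP. That lowers the stakes. It does not remove the point, because the protocol itself fixes which Emax model is primary.

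**Conclusion.** The point holds in a limited form. As worded, the designated primary analysis is most naturally an Emax fit without a patient term. Under the protocol's own SDs its standard errors would then be wrong in two ways: about 3.2 times those of a random-intercept fit for Emax, ED50 and contrasts from the curve, and 0.6 to 0.8 of the true value for the mean curve at about 65 to 120 mg. The mean curve at placebo is about right. The true precision lost is about a factor of 2 for ED50 and 1.0 to 1.8 for dose contrasts. A claim that every mean-curve interval is too narrow, or that all dose comparisons are affected, is not supported.

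The sizes rest on the stated SDs applying to this study, an Emax shape through 0.61 at 65 mg, an assumed ED50 of 15 to 240 mg, and a linear approximation that the simulation bears out. If the primary model does carry a random patient intercept, the error disappears and only the wording and the unexplained widths remain.

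**What to change.** In Section 12.2, define the primary model as log count = E0 + random patient intercept + period + Emax × dose/(ED50 + dose) + error, with Emax and ED50 common to all patients. Period is already in the protocol's own mixed model. Use the same structure when D9120C00020 is added. Otherwise a chance difference between the two groups of patients, with SD about 0.79 × √(1/20 + 1/21) = 0.25 log units, can distort the pooled curve, because 65 mg occurs only in that study. Keep the fit without a patient term at most as a sensitivity analysis.

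In Section 12.3, state which random effects produced 1.73 and 1.43, since a random intercept alone gives about 0.70 to 0.75 and 0.50 to 0.58 under the stated SDs. Then restate the expected precision for the model made primary.

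The cost is a sentence in Section 12.2, a short revision of Section 12.3 and a standard nonlinear mixed-model fit. No extra patients or data are needed. It should be settled before unblinding.
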